3.2.2 Exclusion Criteria

Subjects meeting any of the following criteria will be excluded from the study:

- History of another active malignancy within 3 years, other than basal cell and squamous cell carcinoma of the skin
- Presence of prostate brachytherapy implants unless approved by the PI
- Administration of another radioisotope within five physical half-lives of trial enrollment
- Radiation or chemotherapy within 2 weeks prior to trial enrollment
- Estimated glomerular filtration rate (eGFR) < 15 mL/min/1.73m2
- Serum total bilirubin > 3 times the upper limit of normal

- Aspartate transaminase (AST) or alanine aminotransferase (ALT)> 5 times the upper limit of normal
- Inadequate venous access
- Claustrophobia or any other condition that would preclude PET imaging
- Patients must not be receiving ADT except per criteria directly below. Patients who received in the past must have a serum testosterone that is recovered to at least 100 ng/dL.
 - Patients who have been on ADT +/- novel hormonal agent (NHA) and developed M0CRPC.

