3.5 ASSESSMENT OF INTERVENTION

3.5.1 Imaging Protocol and Follow up

Patients will be intravenously injected with:::; 333 MBq (:::; 9 mCi) of radiotracer approximately 60 minutes prior to image acquisition and will be imaged using the GE Discovery PET-CT scanner at UPMC Hillman Cancer Center, UPMC Magee-Women's Hospital, or UPMC Shadyside Hospital. The scanner will be operated in three-dimensional (3D) emission mode on CT attenuation correction as the case may be and images will be reconstructed with manufacturer-supplied ordered subset expectation maximization iterative methods without point-spread function. The field of view for ¹⁸F-DCFPyL PET scans will be vertex to mid-thigh.

The PET images will be evaluated qualitatively by UPMC Hillman Cancer Center (HCC) nuclear medicine physicians. PET scans will be randomly assigned between five PET readers. Interpreters will have at least more than 5 years of PET interpretation and will interpret images. Double reading will be performed for all the PET scans. The readers will be provided with the recent PSA levels and the type of primary therapy (prostatectomy vs radiation therapy) but will be blinded to all other information. The report will indicate the localization of detected lesions either in the prostate bed, locoregional lymph nodes, distant lymph nodes, bones, and/or visceral organs. A scan will be deemed 'positive' if at least one lesion suggestive of disease recurrence is noted. Prostate lesions and lymph nodes will be considered positive if the uptake in those lesions exceeds blood pool activity. Bone lesions will be recorded as positive if the activity is higher than normal bone marrow uptake.

The UPMC HCC nuclear medicine physicians have extensive experience in interpreting FDG-PET/CT scans including those performed with a variety of agents currently used in the research setting. Scans will be interpreted using HE AW 3.2 Volume Viewer software package.

Visual interpretation:

1. Lymph nodes will be deemed positive if the PET scan uptake is focal and greater than blood pool (adjacent or mediastinal blood pool). Pelvic lymph nodes will be subclassified

- according to their localization as follows: R/L obturator, R/L external iliac, R/L internal iliac and other (total of 7 subgroups).
- 2. Visceral lesions will be considered positive if the uptake is focal and greater than physiologic background activity of the involvement organ or the anatomic location.

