- 3. Bone lesions will be considered positive if the uptake is focal and greater than normal marrow uptake.
- 4. Prostate bed and prostate lesions will be considered positive if uptake is focal and greater than background activity of the prostate.

Follow-up imaging:

A chart review will be performed at 3, 6, 9 and 12 months with a plan to communicate with the referring oncologist team regarding the plan for follow-up imaging with a CT, MRI and/or bone scan. If a follow-up imaging is not obtained by 12 months, then imaging will be requested. Interpretation of follow-up imaging will be performed by local read. The follow-up conventional imaging should be the same modality/modalities as the initial staging work-up to allow for reproducible and accurate comparisons.

PET positive findings will be validated as true or false positive as outlined in more detail below. False negative ¹⁸F-DCFPyL PET findings cannot be determined as this would require biopsies of all PET negative lesions that are present on conventional imaging.

¹⁸F-DCFPyL PET validation will be based on follow-up imaging:

- 1. Lymph nodes will be assessed by change in size. PET positive lymph nodes will be considered:
 - a. True positive:
 - If on follow-up imaging within 3-12 months, lymph nodes seen on CT or MRI scan decrease by more than 30% (for patients undergoing systemic treatment of focal therapy at this site) or increase by more than 20% in short axis diameter (with a minimum of 3 mm in change in size).
 - If patients with solitary lymph node regions show a decrease of PSA by greater than 50% after targeted treatment (i.e. external beam radiation) and the lymph nodes do not change in size (less than 30% decrease or less than 20% increase in short axis diameter).

b. False positive:

• If on follow-up imaging within 3-12 months, sites of initial ¹⁸F-DCFPyL PET positive lymph node lesions seen on CT or MRI scan decrease by more than 30% without systemic therapy or focal therapy at this site.

- If PET positive lymph node lesions do not meet the criteria for above false positive or true positive findings.
- 2. Visceral lesions (non-lymph node soft tissue or organ) will be assessed by change in size. PET positive visceral lesions will be considered:
 - a. True positive:
 - If on follow-up imaging within 3-12 months, visceral lesions seen on CT or MRI scan decrease by 30% (for patients undergoing systemic treatment of focal therapy at this site) or increase by 20% in largest diameter.

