 - If patients with solitary visceral metastasis show a decrease of PSA by greater than 50% after targeted treatment (i.e. external beam radiation) and lesions do not change in size (less than 30% decrease or 20% increase in largest diameter).

b. False positive:

- If on follow-up imaging within 3-12 months, sites of initial PET positive lesions seen on CT or MRI scan decrease by more than 30% without systemic therapy or focal therapy at this site.
- If ¹⁸F-DCFPyL PET positive lesions do not meet the criteria for above false positive or true positive findings.
- 3. ¹⁸F-DCFPyL PET positive bone lesions will be considered:
 - a. True positive:
 - If there was a corresponding positive sclerotic lesion on the CT portion of the ¹⁸F-DCFPyL PET in the same location as the focal uptake.
 - If there is focal uptake seen on the baseline bone scan performed within one month of ¹⁸F-DCFPyL PET.
 - If there is a lesion noted on the initial MRI imaging scan performed within one month of ¹⁸F-DCFPyL PET.
 - If within 12 months follow-up CT scan demonstrates development of sclerosis.
 - If within 12 months follow-up MRI scan demonstrates a new bone lesion.
 - If within 12 months follow-up bone scan demonstrates new focal uptake.

b. False positive:

- If ¹⁸F-DCFPyL PET positive bone lesions do not meet the criteria for true positive findings.
- 4. ¹⁸F-DCFPyL PET positive prostate bed and prostate lesions will be considered:
 - a. True positive:
 - If on follow-up imaging within 12 months, lesions seen on CT or MRI scan decrease by 30% (for patients undergoing systemic treatment of focal therapy at this site) or increase by 20% in largest diameter.

• If patients with prostate bed lesions show a decrease of PSA by greater than 50% after targeted treatment (i.e. external beam radiation) and lesions do not change in size (less than 30% decrease or 20% increase in largest diameter).

b. False positive:

- If on follow-up imaging within 3-12 months, sites of initial ¹⁸F-DCFPyL PET positive lesions seen on CT or **MRI** scan decrease by more than 30% without systemic therapy or focal therapy at this site.
- If ¹⁸F-DCFPyL PET positive lesions do not meet the criteria for above false positive or true positive findings.

Histopathology/Biopsy:

- 1. Localization of lesions for histopathology/biopsy will be classified according to the regions in table (Definition of regions) below.

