Table: Definition of regions

Region	Description
1	Prostate bed
2	Pelvis outside of prostate bed (including LNs)
3	Extra-pelvic soft tissue lesions, LNs, visceral metastases
4	Osseous metastases

3.5.2 Screening Assessments

Patients determined to meet the eligibility criteria to participate in the study will undergo Screening assessments as per the Study Schedule of Activities in Appendix A. The following screening procedures will be performed:

- Informed Consent will be obtained prior to any study-related procedures
- Eligibility assessment per the inclusion and exclusion criteria and diagnosis confirmation
- Subject demographics
- Prostate cancer history
- Vital Signs

- Physical examination, including height, weight, body mass index (BMI) and ECOG performance status assessment
- List of concomitant medications (hormonal agents only)
- Lab assessments

3.5.3 **Procedure for Registration of Subjects**

Patients must not start study activities prior to registration. Subjects can be enrolled after eligibility criteria are met. Registration will require the following information:

- Date of consent
- Participant's name
- Date of birth
- Primary study physician
- Confirmation of eligibility

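### The three PSA-based true-positive rules do not require that no systemic or hormonal therapy was started or changed before the confirming PSA, so a focus that is not cancer can be scored true positive

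*Combined protocol and SAP*

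**What the plan says.** Section 3.5.1 has three true-positive rules that use PSA. Each applies to a lesion whose size has not changed beyond the stated limits.

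- Nodes: "If patients with solitary lymph node regions show a decrease of PSA by greater than 50% after targeted treatment".
- Viscera: "If patients with solitary visceral metastasis show a decrease of PSA by greater than 50% after targeted treatment".
- Prostate bed: "If patients with prostate bed lesions show a decrease of PSA by greater than 50% after targeted treatment (i.e. external beam radiation".

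Bone lesions have no PSA rule. The size-based false-positive rules for nodes, viscera and bed do carry a therapy condition: the lesion must "decrease by more than 30% without systemic therapy or focal therapy at this site". The size-based true-positive rules also mention systemic treatment, as a setting in which shrinkage counts as confirmation. Nodes, viscera and bed each have a catch-all that makes any remaining lesion false positive; for nodes it reads "If PET positive lymph node lesions do not meet the criteria for above false positive or true positive findings".

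The Synopsis and Section 3.10.1 rank the reference standard as histopathology, then imaging, then PSA after local or focal therapy. Section 3.10.1 counts every scanned patient with prostate cancer and rising PSA as evaluable. Section 3.2.2 restricts ADT at entry, with an exception: "Patients who have been on ADT +/- novel hormonal agent (NHA) and developed M0CRPC". Appendix A, footnote d, requires hormonal agents to be recorded before injection only. Footnote g has chart reviews at 3, 6, 9 and 12 months that cover PSA and prostate cancer treatment.

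**The concern.** A PSA fall is evidence about the whole patient. It supports a label for one focus only if the treatment of that focus is the likely cause of the fall. When systemic or hormonal therapy starts in the same interval, PSA can fall because disease elsewhere responds. A size-stable focus that is not cancer then meets the rule and is counted as a true positive. This error runs in one direction and enters the primary endpoint directly.

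The second and smaller issue is the region label. *Solitary* appears in the node and visceral rules, is not defined, and is missing from the bed rule. If bed and nodes are both treated, one PSA fall cannot be assigned to region 1, yet the bed rule as written returns true positive.

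**Working it through.** **Does any text close the gap?**

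- *Entry limit on ADT (Section 3.2.2).* It governs eligibility and says nothing about therapy after the scan.
- *PSA after local or focal therapy (Synopsis, Section 3.10.1).* It suggests that the route was meant for focal treatment, but does not say that this treatment was given alone.
- *Medication recording (Appendix A, footnote d).* Hormonal agents are not required after injection.
- *Chart review (Appendix A, footnote g).* Prostate cancer treatment is reviewed, but no PSA rule uses it.
- *Validation (Section 3.10.1).* Local investigators apply the prespecified criteria, so the literal rule decides, and it returns true positive.

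**What could solitary mean?** For nodes, the text supports at least three readings: one of the pelvic subgroups ("R/L obturator, R/L external iliac, R/L internal iliac and other (total of 7 subgroups"), one of the four regions in the table (for example "Pelvis outside of prostate bed (including LNs"), or no other PET-positive region at all.

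**The plan's own precision figure (Section 3.10.2).** 300 × 0.85 = 255 positives. Exact (Clopper-Pearson) 95% intervals with n = 255:

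| Count | PPV | Exact 95% CI | Plan's row |
|---|---|---|---|
| 204 | 80.0% | 74.6-84.7 | 75-85 |
| 214 | 83.9% | 78.8-88.2 | 79-88 |
| 225 | 88.2% | 83.6-91.9 | 84-92 |
| 235 | 92.2% | 88.1-95.1 | 88-95 |
| 245 | 96.1% | 92.9-98.1 | 93-98 |
| 255 | 100% | 98.6-100 | 99-100 |

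All six rows reproduce. The widest is 10.2 points, so the stated width of less than 12% holds over the tabulated range.

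**Illustrative size of the inflation.** Assumptions, none from trial data:

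- 204 of 255 are true positive as the rules now stand.
- A patient is true positive if any lesion is.
- k patients are true positive only through a PSA rule with newly started or changed systemic therapy.
- A share f of the k are not cancer. The values 0.12 and 0.20 are 1 minus the 88% and 80% rows of the plan's table, used only as round figures; those rows describe all positives, not this subgroup.

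Inflation = k × f / 255:

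- k = 10: 1.2 to 2.0 patients, 0.5 to 0.8 points.
- k = 25: 3 to 5 patients, 1.2 to 2.0 points.
- k = 50: 6 to 10 patients, 2.4 to 3.9 points. This k is nearly a quarter of all true positives (50/204 = 24.5%) and is an upper stress case.

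**Precision if the k become indeterminate.** Each is a true positive under the current text, so numerator and denominator both lose k:

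| Lost | Count | PPV | CI width (points) |
|---|---|---|---|
| 0 | 204/255 | 80.0% | 10.2 |
| 10 | 194/245 | 79.2% | 10.5 |
| 25 | 179/230 | 77.8% | 11.1 |
| 44 | 160/211 | 75.8% | 11.97 |
| 45 | 159/210 | 75.7% | 12.02 |
| 50 | 154/205 | 75.1% | 12.3 |

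If the same patients are counted as false positives, PPV is 194/255 = 76.1% for k = 10 and 179/255 = 70.2% for k = 25. These are bounds, since they treat every such focus as not cancer.

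**The case against.** The best defence is that the PSA route was written for focal treatment. The PSA rules name only targeted treatment with radiation as the example, the Synopsis and Section 3.10.1 speak of PSA after local or focal therapy, and the size-based true-positive rules name systemic treatment where a response to it is admitted. On that reading the plan never meant to accept a systemic response, and only the word *alone* is missing. This is a fair account of intent, but a local investigator who applies the text literally must still score true positive.

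The route is also narrow. It opens only where histology does not decide, the focus received targeted treatment and its size is stable. Bone is outside it. That limits the size and stands.

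Three stronger readings are tempting and are not supported:

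- *The reference standard as a whole overstates PPV.* The catch-all rules make unconfirmed lesions false positive, which pushes the other way. The net direction is not fixed.
- *Combined therapy is shown to be common.* Section 1.1 reports that 58 of 131 management changes in the earlier phase 3 study of this tracer were from salvage local to systemic therapy. That is a switch, not use of both, and patients who left local therapy would not enter this route.
- *The missing word solitary biases the primary endpoint.* Where no systemic therapy intervenes, a PSA fall after several regions are treated can still support a patient-level true positive. The damage is to the region label, and nothing in the documents allows it to be quantified.

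**Conclusion.** The point holds as a gap in a stated classification rule for the primary endpoint. It should be corrected before labels are assigned. Under the literal text, a size-stable focus that is not cancer can be scored true positive when systemic or hormonal therapy is started or changed before the confirming PSA, and no other section prevents this. The isolated effect is upward on per-patient and per-region PPV.

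The magnitude cannot be known from the documents. The scenarios above give 0.5 to 2.0 points for 10 to 25 affected patients, and they rest wholly on the assumed k and f. The plan's sample-size arithmetic is correct and is not in question. The undefined and unevenly applied *solitary* is a lesser point, confined to the secondary endpoint and unquantified.

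**What to change.** These changes affect classification only; treatment is untouched.

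1. In all three PSA rules, let the fall confirm a lesion only if no systemic or hormonal therapy was newly started or changed between the PET and the confirming PSA. Unchanged background ADT in M0 CRPC does not disqualify. State in advance which PSA is the baseline and which is the confirming value; the rules now specify neither.
2. Define *solitary* as the only PET-positive region and apply it to the bed rule for the region label. The per-patient label is unaffected.
3. Make indeterminate those lesions that are true positive under the current text and are barred only by items 1 or 2, so that they do not fall into the false-positive catch-all. A patient is indeterminate only if barred by item 1 with no lesion true positive by another route. Name the PPV excluding indeterminates as primary, report the PPV counting them as false positive as a sensitivity bound, and amend the evaluability sentence in Section 3.10.1 to match.
4. Report PPV by type of verification, with a sensitivity PPV that excludes true positives confirmed by PSA alone.

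**Cost.** Therapy start and change dates must be recorded at chart reviews that already cover PSA and treatment. The main downside is precision: only true positives leave the denominator, so PPV cannot rise and the interval widens. From an assumed 204/255, the planned width of less than 12% survives 44 losses and fails at 45, so Section 3.10.2 should acknowledge this. One limit remains: the condition does not remove PSA falls caused by other disease within the treated field, which is a further reason for item 4.

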3.2 SELECTION OF STUDY POPULATION

3.2.1 Inclusion Criteria

To be eligible to participate in this trial, subjects must meet all of the following criteria:

- Histologically confirmed diagnosis of prostate cancer
- Biochemical recurrence was defined as a PSA of 0.2 or more ng/mL measured more than 6 weeks after prostatectomy or a PSA of 2 or more ng/mL rise above nadir following radiation therapy (ASTRO Phoenix consensus definition) [59]
 - If PSA values are reported in double decimal points, it will be rounded to the nearest single value decimal point (e.g., 0.14 will be rounded to 0.1 and 0.15 -0.19 will be rounded to 0.2)
- Age 2: 18 years of age
- Eastern Cooperative Oncology Group (ECOG) performance status::; 2 (Kamofsky 2: 60%)
- Ability to understand and willingness to sign a written informed consent document
- Willing to comply with clinical trial instructions and requirements

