3.10 STATISTICAL METHODS PLANNED IN THE PROTOCOL AND DETERMINATION OF SAMPLE SIZE

3.10.1 Study Design

This is a single arm phase II clinical trial to evaluate the positive predictive value (PPV) of ¹⁸F-DCFPyL PET imaging in men diagnosed with prostate cancer with increasing prostate-specific antigen (PSA) levels. PPV is the number of true positives (TP) divided by number of patients who are tested positive (i.e., TP + FP) based on the PET imaging. The determination of TP and positive testing is detailed in Section 3.5.1. Secondary endpoints are PPV of ¹⁸F-DCFPyL PET (per-region). All patients who are diagnosed with prostate cancer with increasing PSA levels and who have received PET scans will be evaluable for the analysis.

All patients will be followed up for histopathologic analysis, conventional imaging (CT, MRI and/or bone scan) and/or serum PSA after focal salvage therapy acquired during clinical routine. Combination of (in descending priority) histopathologic analysis, imaging, and PSA follow-up after local/focal therapy will used for lesion validation. Validation will be performed by the unblinded local investigators after reviewing images and reports, following prespecified criteria of the study protocol. In patients with follow-up, positive ¹⁸F-DCFPyL PET findings will be validated as true or false-positive results. Region negative on ¹⁸F-DCFPyL PET, but with subsequently confirmed prostate cancer by histopathologic analysis, will be considered false-negative results. True negative will not be defined. (please see section 3.5.1. for details).

3.10.2 Sample Size

A total of 300 evaluable participants will be enrolled into this study. We expect approximately 85% of them, i.e., 255 patients, will have positive test results. Based on these 255 patients, the exact 95% confidence interval (CI) for PPV has a width ofless than 12%. The following table shows the exact 95% CI corresponding to different observed PPV values.

Observed PPV	95% CI of true underlying PPV
80%	(75%, 85%)
84%	(79%, 88%)
88%	(84%, 92%)
92%	(88%, 95%)
96%	(93%, 98%)
100%	(99%, 100%)

As an example, from this table, an observed 80% PPV value indicates that we can be 95% confident that the true underlying PPV lies in the interval (75%, 85%). If the observed PPV is 88%, then we can be 95% confident that the true underlying PPV lies in the interval (84%, 92%).

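### The PSA route to true positive for local lesions names only the prostate bed, so read literally a treated, size-stable lesion in an intact prostate defaults to false positive

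*Combined protocol and SAP*

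**What the plan says.** Section 3.5.1 sets the rules by which PET-positive findings become true or false positives. Item 4 opens with "PET positive prostate bed and prostate lesions will be considered", so it governs both sites. It offers two routes to true positive:

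- **Imaging.** Under treatment, "lesions seen on CT or MRI scan decrease by 30% (for patients undergoing systemic treatment of focal therapy at this site"); otherwise a 20% increase in largest diameter.
- **PSA.** "If patients with prostate bed lesions show a decrease of PSA by greater than 50% after targeted treatment", combined with stable size: "lesions do not change in size (less than 30% decrease or 20% increase in largest diameter").

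There are two false-positive bullets. The first covers a shrinkage of more than 30% without therapy. The second is a catch-all that applies if "PET positive lesions do not meet the criteria for above false positive or true positive findings".

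Men who still have a prostate are eligible: section 3.2.1 admits "a PSA of 2 or more ng/mL rise above nadir following radiation therapy (ASTRO Phoenix consensus definition"). Section 3.10.1 ranks the evidence as histopathology, then imaging, then PSA. It says that "PSA follow-up after local/focal therapy will used for lesion validation", without restricting the site, and assigns validation to unblinded local investigators applying the prespecified criteria.

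The terms are not used uniformly. The visual interpretation rule names both sites ("Prostate bed and prostate lesions will be considered positive if uptake is focal and greater than background activity of the prostate"), as does the secondary objective in section 2.2. The list of report locations in section 3.5.1 gives the prostate bed and no prostate, and the region table labels Region 1 as prostate bed only.

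**The concern.** The PSA bullet is narrower than the heading above it, and the item ends in a catch-all. A lesion that the bullet omits is therefore classified as a false positive; it is not left unclassified. On the literal text, the class of a treated, size-stable local lesion depends on whether the patient still has his prostate, which follows from his primary therapy and not from what the tracer detected.

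At stake are the prostate or prostate-bed component of the secondary endpoint and, to a lesser and unknown extent, the primary per-patient PPV. If validators read the bullet differently, like records could also be scored differently within the same trial.

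**Working it through.** **1. Trace one record through item 4.** Take an illustrative patient with targeted treatment, PSA 3.0 to 0.6 ng/mL, largest diameter 12 to 11 mm, and no decisive histology.

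- PSA change: (0.6 − 3.0)/3.0 = −80%, beyond the 50% fall required.
- Size change: (11 − 12)/12 = −8.3%, inside the stable band.

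| Criterion in item 4 | Prostate bed lesion | Intact-prostate lesion, literal reading |
|---|---|---|
| TP: 30% decrease under treatment, or 20% increase | not met | not met |
| TP: PSA fall above 50%, stable size | met | not met (site not named) |
| FP: decrease above 30% without therapy | not met | not met |
| FP: catch-all | not reached | applies |
| **Class** | **true positive** | **false positive** |

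**2. Compare with the other sites.** Lymph nodes (item 1) and visceral lesions (item 2) are also judged by size change, and each has a PSA route, limited to solitary nodal regions or a solitary visceral metastasis. Bone (item 3) has no PSA route but is not judged by size change. On the literal reading, the intact prostate is the only size-assessed site with no PSA route. The protocol gives no reason.

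**3. Reproduce the planned precision.** Expected positives are 0.85 × 300 = 255. Exact (Clopper-Pearson) 95% intervals at 255:

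| Observed PPV | Count | Computed | Plan (3.10.2) |
|---|---|---|---|
| 80% | 204 | 74.6–84.7 | 75–85 |
| 84% | 214 | 78.8–88.2 | 79–88 |
| 88% | 224 | 83.2–91.6 | 84–92 |
| 92% | 235 | 88.2–95.1 | 88–95 |
| 96% | 245 | 92.9–98.1 | 93–98 |
| 100% | 255 | 98.6–100 | 99–100 |

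The table is reproduced to the whole percent, apart from the lower limit at 88%. That difference depends on the integer chosen: 225/255 gives 83.6–91.9, which rounds to the plan's figures.

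**4. Effect per reclassified patient.** Moving one patient from TP to FP leaves the denominator unchanged, so per-patient PPV falls by 1/255 = 0.39 points. For the regional PPV the fall is 1/m, where m is the number of positives validated in Region 1. The documents do not give m.

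**5. Illustration only.** The protocol does not give the share of men with an intact irradiated prostate. Section 1.1 reports 15% radiation-only in the earlier phase 3 recurrence study. Assuming that share here gives 0.15 × 255 = 38.25, about 38 men. The fraction meeting every condition (treated prostate lesion, PSA fall above 50%, stable size, no decisive histology, no other true-positive lesion) is unknown. Assume 5% to 50%, starting from 224/255 = 87.8% with the PSA route open:

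| Assumed fraction of 38.25 | Patients | Literal PPV | Exact 95% CI | Fall (points) |
|---|---|---|---|---|
| 5% | 2 | 222/255 = 87.1% | 82.3–90.9 | 0.8 |
| 10% | 4 | 220/255 = 86.3% | 81.4–90.3 | 1.6 |
| 25% | 10 | 214/255 = 83.9% | 78.8–88.2 | 3.9 |
| 50% | 19 | 205/255 = 80.4% | 75.0–85.1 | 7.5 |

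The spread shows that the result is driven by an assumption for which the documents give no value.

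**The case against.** The strongest reply is that prostate bed is shorthand for the local site. The region table and the report locations both use it that way, and an early sentence of section 3.5.1 does the reverse, naming only prostate lesions. Read strictly throughout, an intact-prostate lesion would have no place in the report list and no Region 1 to fall into, which can hardly be meant. On the shorthand reading the PSA bullet inherits the scope of its heading, agrees with section 3.10.1 and misclassifies nobody. This stands as a plausible reading. It does not remove the defect, because the heading names both sites and the bullet beneath it names one. The choice then falls to an unblinded validator told to follow prespecified criteria.

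Three further points stand and limit the concern:

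- Histology ranks first and is sought where feasible, and a 30% decrease under treatment still confirms an intact-prostate lesion. Only treated, size-stable lesions without decisive histology are exposed.
- A reader might infer that every man recurring after radiation is affected. He is not. In the earlier study 35% had prostatectomy and radiation, and such men have a prostate bed. Brachytherapy implants are also excluded unless approved.
- The restriction may be deliberate. PSA routes elsewhere are narrow and bone has none. The documents do not say.

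**Conclusion.** The inconsistency between the item 4 heading and its PSA bullet is real. On the literal text it gives a class that depends on whether the prostate is in place. On the shorthand reading it does not. The supportable conclusion is that the classification rule is ambiguous, with a one-directional risk: any error turns true positives into false positives and lowers PPV. The regional PPV for prostate or prostate bed is the most exposed. The per-patient PPV moves only if the patient has no other true-positive lesion. This assumes that one true-positive lesion makes the patient a true positive, which the plan does not spell out.

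A reader might go further and infer that the primary PPV will be biased down by an amount that rivals the planned interval half-width of about 4 to 5 points. The documents do not support that. The radiation-only share is borrowed from another trial, and no source is given for the rates of further targeted treatment, PSA response, stable size or missing histology. The number of men affected cannot be determined; only the 0.39 points per reclassified patient is firm. The planned sample size and interval table are unaffected. The wording should be corrected because the remedy is cheap and the class of a primary-endpoint lesion should not rest on interpretation.

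**What to change.** Before lesions are validated:

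1. In section 3.5.1, item 4, true positive, second bullet, extend the site to patients with prostate bed or prostate lesions, so that it matches the item heading and the unrestricted site in section 3.10.1.
2. Use the same term for Region 1 in the region table and in the list of report locations in section 3.5.1.
3. If the exclusion of intact-prostate lesions was intended, say so and give the reason. In that case do not let such lesions become false positives merely because no PSA route exists for them.

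The cost is a few words in the protocol. PSA levels and treatment are already collected by chart review (Appendix A, footnote g), so no visit, data item or sample-size change is needed. The downside is small: some intact-prostate lesions will rest on PSA evidence, as prostate-bed lesions already do. Making the change after classes are known would look outcome-driven, so it should come first.
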